1.0 TRIAL SUMMARY

Abbreviated Title	Lenvatinib plus pembrolizumab in patients with immune checkpoint inhibitor naïve metastatic uveal melanoma
Trial Phase	Phase II
Clinical Indication	Treatment of participants with immune checkpoint inhibitor naïve metastatic uveal melanoma
Trial Type	Interventional
Type of control	n/a
Route of administration	Oral and IV
Treatment Groups	Single arm: Lenvatinib 20 mg daily plus pembrolizumab 200 mg IV every 3 weeks.
Number of trial participants	30
Estimated enrollment period	20 months
Estimated duration of trial	48 months (FPFV to LPLV)
Duration of Participation	Subjects will participate in the clinical trial from the time of signing the ICF until the final protocol specified contact. Subjects who discontinue treatment for reasons other than disease progression or treatment related toxicity will have post-treatment follow-up until documented radiographic evidence of disease progression (per iRECIST), initiation of a subsequent anti-cancer therapy, death, pregnancy, withdrawal of consent, lost to follow up or the end of the clinical trial.
Estimated average length of treatment per patient	6 months

2.0 TRIAL DESIGN

2.1 Trial Design

This is a phase II, single arm, single institution clinical trial. Adults (age \geq 18 years-old) with immune checkpoint inhibitor naïve metastatic uveal melanoma will be evaluated for eligibility. Eligible participants will be treated with the combination of Lenvatinib 20 mg daily + pembrolizumab 200 mg IV every 3 weeks for a maximum of 2 years.

2.2 Trial Schema

Patient population Immune checkpoint inhibitor naïve metastatic uveal melanoma *N* = 30

Lenvatinib 20 mg/day plus Pembrolizumab 200 mg q3 weeks

Objectives

Primary:

- progression free survival Secondary:
- Objective response rate
- Overall survival
- Safety/tolerability

2.3 Schedule of Activities

Table 1 Study Schedule of Activities

Study Period:	Scre	ening	Intervention (21-Day Cycles)											Post	treatment Vis	sits	Notes
Visit Number/Title: Cvcle Dav	1/Scre	ening	1	C1 8	15	1	C2	C3	C4	C5	C6 to C35	\geq C36	End of Treatment	Safety Follow- up	Efficacy Follow- up	Survival FU	
Scheduling Window (days)	-42 to - 1	-28 to - 1	±3	±3	±3	±3	±3	±3	±3	±3	±3	±3	At time of treatment discontin uation	Approx. 30d after last dose (± 7d)	$\begin{array}{c} -r \\ Q6W \\ (Y1) \text{ or } \\ Q9W \\ (Y2+) \\ (\pm 7d) \end{array}$	Q12W ^a (± 14d)	
Administrative Proced	ures												•		•		
Informed Consent	Х																
Inclusion/Exclusion Criteria		Х															
Demographics and Medical History		Х															Includes smoking and tobacco use.
Prior Treatment		Х															
Prior/Concomitant Medication Review		Х	Х	Х	Х	Х	Х	Х	Х	х	X	Х	Х	Х			
Subsequent Antineoplastic Therapy Status													Х	Х	Х	Х	
Survival Status			•													X	Participants may be contacted for survival status at any time during the course of the study.

Confidential

Study Dariod	Sara	oning	Intervention (21-Day Cycles)											Doct	traatmant Vi	sita	Notos
Study Period:	Scree	ening			11	nterve	ntion	(21 - D	ay Cy	cies)	C6		F 1 C	Post	treatment vi	SILS	Inotes
Visit Number/Title:	1/Scre	eening		C1		C	22	C3	C4	C5	to C35	≥ C36	Treatment	Safety Follow-	Efficacy Follow-up	Survival FU	
Cycle Day		1	1	8	15	1	15	1	1	1	1	1		up			
Scheduling Window (days)	-42 to - 1	-28 to - 1	±3	±3	±3	±3	±3	±3	±3	±3	±3	±3	At time of treatment discontin uation	Approx. 30d after last dose (± 7d)	Q6W (Y1) or Q9W (Y2+) (± 7d)	Q12W ^a (± 14d)	
Study Intervention Ad	ministra	tion	1	1									1				
Lenvatinib Dispensing			Х			Х		Х	Х	Х	Х	Х					
Lenvatinib Administration PO QD			-		L		L	L	L								Taken at home
Lenvatinib container returned						X		X	X	X	Х	Х					Lenvatinib will be held for 7 days prior to biopsy and will resume 2 days post biopsy.
Pembrolizumab Administration IV Q3W			x			X		Х	X	X	Х						
Efficacy Procedure																	
Tumor Biopsy Collection		Х						Xc									Fresh tumor biopsy specimens will be collected at Screening and at C3D8 from at least 15 subjects (in no certain order). Archival tissue may be used in place of pre- treatment biopsy.
Tumor Imaging (chest, abdomen, & pelvis) and iRECIST Assessment Note: Imaging of the brain required only at screening.		Х							X		Х	X	X		X		Imaging is performed at Screening, Week 9 and every 9 weeks (± 7 days) during Year 1. After Year 1, imaging is performed every 12 weeks (±7 days). This schedule will be maintained regardless of treatment delays.

Confidential

Study Period:	Scre	ening			Ι	nterve	ention	(21-D	ay Cy	cles)				Post	treatment Vis	sits	Notes
Visit Number/Title:	1/Scro	eening	1	C1	15	(22	C3	C4	C5	C6 to C35	\geq C36	End of Treatment	Safety Follow-	Efficacy Follow-	Survival	
Scheduling Window (days)	-42 to - 1	-28 to - 1	±3	8 ±3	±3	±3	±3	±3	±3	±3	±3	±3	At time of treatment discontin uation	Approx. 30d after last dose (± 7d)	up Q6W (Y1) or Q9W (Y2+) (± 7d)	Q12W ^a (± 14d)	
Safety Procedures	1	1	r –	1	r	r –	r	r –	r –	1		r	1	1	1	Γ	
AE/SAE Review	x	x	x	x	x	x	x	x	x	x	x	x	x	х	х		Report AEs occurring within 30 days after the last dose of study intervention. Report SAEs occurring within 90 days after the last dose of study intervention, or 30 days after the last dose of study intervention if a new anticancer therapy is initiated, whichever is first.
Full Physical Examination		Х											X				
Height		Х															
Directed Physical Examination			X		Х	X	Х	X	X	Х	Х	Х		Х			
Contact				x													The investigator or medically qualified designee (consistent with local requirements) will assess participants for development of early toxicity. An unscheduled visit can occur before C1D15 if necessary for safety.

Study Period	Scre	ening			I	nterve	ntion	(21-D	av Cv	cles)				Post tr	eatment Visi	its	Notes
Study Ferrou.	Sere	creening In					ntion				C6		_End of	1 050 0			10005
Vigit Number/Title:	1/50%	onina		C1		0	r'n	C2	C4	C5	to	\geq	Treatment	Safety	Efficacy	Second and	
Cvcle Dav	1/501	Jenning	1	8	15	1	15	1	1	1	1	1		Follow-	Follow-	FU	
Scheduling Window (days)	-42 to - 1	-28 to - 1	±3	±3	±3	±3	±3	±3	±3	±3	±3	±3	At time of treatment discontin uation	Approx. 30d after last dose (± 7d)	Q6W (Y1) or Q9W (Y2+) (± 7d)	Q12W ^a (± 14d)	
Vital Signs (resting BP, heart rate, RR, and temp) and weight		х	x		x	x	х	х	x	х	Х	Х	X	х			The Day 15 visit is mandatory for C1 and C2. During C3 and subsequent cycles, participants may return for the D15 visit if BP monitoring is required.
12-lead ECG with QTcF Determination (Single)		X	x			х					X	X	X	Х			Every 4 cycles. ECG at Screening, C1D1, C2D1, D1of every fourth cycle (12 weeks) thereafter (e.g., C6, C10, C14, etc.), EOT, and safety follow-up. For high-risk participants (Section 6.1.2.7), conduct ECG monitoring every cycle. If Lenvatinib is discontinued, ECGs are only required at the EOT and Safety Follow-up visits.

Study Pariod:	Scra	aning			T	ntarria	ntion	(21 D	ov Cv	alec)				Post t	eatment Visits		Notes
Study I eriod.	5010	ennig					mion	(21-D	ay Cy		C6		End of	1 05t ti			INDIES
Visit Number/Title:	1/Scr	ening		C1		C	r7	C3	C4	C5	to C25	≥ C36	Treatment	Safety Fallow	Efficacy	Survival	
Cycle Day	1/501	coning	1	8	15	1	15	1	1	1	1	1		up	ronow-up	10	
Scheduling Window (days)	-42 to - 1	-28 to - 1	±3	±3	±3	±3	±3	±3	±3	±3	±3	±3	At time of treatment discontin uation	Approx. 30d after last dose (± 7d)	Q6W (Y1) or Q9W (Y2+) (± 7d)	Q12W ^a (± 14d)	
MUGA Scan or ECHO		х												Х			Additional LVEF assessments may be performed as clinically indicated.
ECOG Performance Status		X*	X			X		х	х	X	Х	Х	Х	Х			Performance status obtained on C1D1 may also be used as the screening value to determine eligibility. *Screening ECOG within 7 days before initiation of study intervention. If performed within 7 days prior to day one ECOG does not need to be repeated on Day 1
Laboratory Procedure	s/Asses	sments	(Loca	ıl Lat	orate	ory)			1	1	1	1		1	I		
Serum β-hCG Pregnancy Test (WOCBP only)		х				X		X	X	X	х	Х	Х	X			WOCBP require a negative test. If more than 24 hours have elapsed before the first dose of study intervention, another pregnancy test is required. A serum pregnancy test will be performed per Appendix 2.

Study Period:	Scree	ening			I	nterve	ntion	(21-D	ay Cy	cles)				Post ti	eatment Visits	5	Notes
Visit Number/Title:	1/Scre	Screening		C1		0	22	C3	C4	C5	C6 to C35	≥ C36	End of Treatment	Safety Follow-up	Efficacy Follow-up	Survival FU	
Cycle Day			1	8	15	1	15	1	1	1	1	1		-	-		
Scheduling Window (days)	-42 to - 1	-28 to - 1	±3	±3	±3	±3	±3	±3	±3	±3	±3	±3	At time of treatment discontin uation	Approx. 30d after last dose (± 7d)	Q6W (Y1) or Q9W (Y2+) (± 7d)	Q12W ^a (± 14d)	
Serum FSH (WONCBP only)		Х															In the absence of 12 months of amenorrhea, confirmation with 2 FSH measurements in postmenopausal range is required.
HIV, Hepatitis B, and Hepatitis C		X*															*Required at Screening only if mandated by local health authority
Hematology		X*	х		х	х		х	x	x	Х	Х	Х	Х			Labs obtained on C1D1 may also be used as the screening value to determine eligibility.
Chemistry		X*	х		х	x		х	х	х	Х	Х	Х	х			*Perform screening laboratory tests within 7 days before the first dose. If performed within 7 days prior to day one CMP does not need to be repeated on Day 1
Thyroid Function Tests (LDH, Free T4, TSH)		X*	x			x			x		x	X		X			Labs obtained on C1D1 may also be used as the screening value to determine eligibility. *Perform screening laboratory tests within 7 days before first dose, then at C2 and every 2 cycles thereafter (C4, C6, etc.) If performed within 7 days prior to day one thyroid function and LDH does not need to be repeated on Day 1

Confidential

Study Period:	Scree	ening		Intervention (21-Day Cycles)				Post t	reatment Visit	S	Notes						
Visit Number/Title: Cycle Day	1/Scro	eening	1	C1 8	15	C	2 15	C3	C4	C5	C6 to C35 1	\geq C36	End of Treatment	Safety Follow- up	Efficacy Follow-up	Survival FU	
Scheduling Window (days)	-42 to - 1	-28 to - 1	±3	±3	±3	±3	±3	±3	±3	±3	±3	±3	At time of treatment discontin uation	Approx. 30d after last dose (± 7d)	Q6W (Y1) or Q9W (Y2+) (± 7d)	Q12W ^a (± 14d)	
Urine Dipstick Testing		X*	x		x	X	x	x	x	X	x	x	х				After C1, collect samples at C1D15 and C2 D15 and up to 3 days before D1 of each cycle. If lenvatinib is discontinued, urine dipstick testing no longer required. Urine dipstick testing (or urinalysis) obtained and reviewed on C1D1 may also be used as the screening value to determine eligibility. If 24-hour urine collection for quantitative assessment of proteinuria is required, C1D1 is postponed to after proteinuria result available. *Perform screening urinalysis tests within 7 days before the first dose. If performed within 7 days prior to day one urine dipstick does not need to be repeated on Day 1

Study Period:	Scree	ening			I	nterve	ntion	(21 - D	ay Cy	cles)	1		Endof	Post tr	eatment Visi	its	Notes
Visit Number/Title: Cycle Day	1/Scre	eening	1	C1 8	15	C	2	C3	C4	C5	C6 to C35 1	≥ C36	Treatment	Safety Follow-up	Efficacy Follow- up	Survival FU	
Scheduling Window (days)	-42 to - 1	-28 to - 1	±3	±3	±3	±3	±3	±3	±3	±3	±3	±3	At time of treatment discontin uation	Approx. 30d after last dose (± 7d)	Q6W (Y1) or Q9W (Y2+) (±7d)	Q12W ^a (± 14d)	
INR or PT and aPTT		X*	x														Labs obtained and reviewed on C1D1 may also be used as the screening value to determine eligibility. Additional testing is to be performed as clinically indicated for participants taking anticoagulants. *Perform screening laboratory tests within 7 days before the first dose. If performed within 7 days prior to day one INR or PT and aPTT does not need to be repeated on Day 1
Biomarkers																	
Blood for Research	Х		Xb			х		х	Х	х	Х						Collect at screening and pre dose on D1 of Cycles 1-6.
Optional Specimen for Banking	Х		Xb			Х		Х	Х	Х	Х						Optional blood collection for specimen banking, collect at screening and pre dose on D1 of Cycles 1-6.
Abbreviations: AE = ad	verse ev	vent; aP	TT =	activa	ted pa	artial	throm	bopla	stin tir	ne; BI	P = bloc	od press	sure; β-HCG	$s = \beta$ human c	horionic gon	adotropin; C =	= cycle; CXDY= Cycle X Day Y;

Abbreviations: AE = adverse event; aPTT = activated partial thromboplastin time; BP = blood pressure; β -HCG; = β human chorionic gonadotropin; C = cycle; CXDY= Cycle X Day Y; d = day; ECG = electrocardiogram; ECOG = Eastern Cooperative Oncology Group; ECHO = echocardiogram; EOT = end of treatment; FSH = follicle-stimulating hormone; FU = follow-up; HIV = human immunodeficiency virus; INR = international normalized ratio; LVEF = left ventricular ejection fraction; MUGA = multigated acquisition; PT = prothrombin time; Q6W = every 6 weeks; Q9W = every 9 weeks; Q12W = every 12 weeks; QTcF = QT interval corrected with Fridericia's formula; RNA= ribonucleic acid; RR = respiratory rate; SAE = serious adverse event; SoA= schedule of activities; T4 = thyroxine; TSH = thyroid-stimulating hormone; WOCBP = women of childbearing potential; WONCBP = women of nonchildbearing potential.

a. If the poststudy visit occurs less than 14 days after the last dose of study intervention, a subsequent follow-up telephone call should be made at 14 days post the last dose of study intervention to determine of any AEs have occurred since the poststudy clinic visit.

b. Correlative and optional specimen banking samples collected for Screening may be used for C1D1 if the collection is within 3 days prior to C1D1. c. Collect at C3D8

3.0 OBJECTIVE(S), HYPOTHESIS(ES), AND ENDPOINT(S)

3.1 **Primary Objective(s), Hypothesis(es), and Endpoint(s)**

(1) **Objective:** To evaluate the effect of lenvatinib + pembrolizumab on progression free survival.

Hypothesis: Treatment with Lenvatinib + pembrolizumab will result in improved progression free survival as compared with previously reported systemic therapies including pembrolizumab monotherapy, ipilimumab + nivolumab and tebentafusp.

Primary Endpoint: Progression free survival, defined as the time from enrollment to the first documented evidence of disease progression or death.

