3.2 Secondary Objective(s), Hypothesis(es), and Endpoint(s)

(1) **Objective**: To evaluate the objective response rate resulting from treatment with Lenvatinib + pembrolizumab.

Hypothesis: Treatment with Lenvatinib + pembrolizumab will result in an improved objective response rate as compared with previously reported therapies including pembrolizumab monotherapy, ipilimumab + nivolumab and tebentafusp.

Secondary Endpoint: Objective response rate (complete and partial responses assessed by iRECIST)

(2) **Objective**: To evaluate the effect of treatment with Lenvatinib + pembrolizumab on overall survival.

Hypothesis: Treatment with Lenvatinib + pembrolizumab will result in improved overall survival as compared with previously reported therapies including pembrolizumab monotherapy, ipilimumab + nivolumab and tebentafusp.

Secondary Endpoint: Overall survival, defined as the time from enrollment to death (resulting from any cause).

(3) **Objective**: To evaluate the safety and tolerability of treatment with Lenvatinib + pembrolizumab in patients with metastatic uveal melanoma.

Hypothesis: Treatment with Lenvatinib + pembrolizumab will demonstrate an acceptable toxicity profile in patients with metastatic uveal melanoma.

Secondary Endpoint:

• Adverse events (per CTCAE v5.0)

• Frequency of treatment interruption, dose reduction, and treatment discontinuation due to treatment related adverse events (TRAE).

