4.0 BACKGROUND & RATIONALE

4.1 Background

Uveal melanoma

Metastatic uveal melanoma is associated with a very poor prognosis with median survival of 6-12 months [1]. Unfortunately, systemic therapy with immune checkpoint inhibitors has demonstrated inadequate efficacy. In a phase II clinical trial with ipilimumab, no objective responses were observed and the median progression free survival (PFS) was 2.8 months [2]. A small phase II clinical trial (17 patients) evaluated the efficacy of pembrolizumab monotherapy. Two out of the 17 patients had an objective response (11.7%) and median PFS was 3.8 months [3]. Treatment with the combination of ipilimumab + nivolumab was evaluated in a phase II clinical trial that showed an objective response rate (ORR) of 18% with median PFS of 5.5 months and median overall survival of 19.1 months [4]. The results of the phase III clinical trial evaluating the bispecific fusion protein Tebentafusp in patients with metastatic uveal melanoma were reported at the 2021 AACR annual meeting. In this clinical trial, patients were randomly assigned (2:1) to either treatment with tebentafusp or investigator choice of therapy (pembrolizumab, ipilimumab or dacarbazine). The authors reported a median overall survival of almost 22 months for tebentafusp compared with 16 months in the investigator choice arm. Tebentafusp resulted in an ORR of 9% [5]. As such, effective therapies for patients with metastatic uveal melanoma represents a significant unmet clinical need.

Pembrolizumab is a potent humanized immunoglobulin G4 (IgG4) monoclonal antibody (mAb) with high specificity of binding to the programmed cell death 1 (PD-1) receptor, thus inhibiting its interaction with programmed cell death ligand 1 (PD-L1) and programmed cell death ligand 2 (PD-

L2). Based on preclinical in vitro data, pembrolizumab has high affinity and potent receptor blocking activity for PD-1. Pembrolizumab has an acceptable preclinical safety profile and is in clinical development as an intravenous (IV) immunotherapy for advanced malignancies. Keytruda[®] (pembrolizumab) is indicated for the treatment of patients across a number of indications because of its mechanism of action to bind the PD-1 receptor on the T cell. For more details on specific indications refer to the Investigator brochure (IB).

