7.0 STATISTICAL ANALYSIS PLAN

7.1 Statistical Analysis Plan Summary

For this exploratory pilot study, sample size was calculated based on a hypothesis of anticipated clinical efficacy and compared with historical clinical trial data. As this is a single arm study, no formal statistical comparisons will be made.

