7.2 Statistical Analysis Plan

This represents a single-arm signal finding pilot study. As such, no formal statistical comparisons will be conducted. However, using historical data from prospective clinical trials and retrospective case series reported in the literature, therapy with PD-1 inhibitors results in objective response rates of approximately 10% and median progression free survival of approximately 3.5 months (reviewed by Wessely A., et al. International Journal of Molecular Sciences 2020) [27].

In this 30 patient pilot study, using a one-sided test with a type I error of 0.05, the power for detecting a difference in the ORR compared with the historical average of 10% ORR with anti-PD-1 monotherapy varies with the hypothetical experimental ORR as follows:

Hypothetical experimental ORR	Historical average ORR	Power
20%	10%	0.55
25%	10%	0.78
30%	10%	0.91

Interim futility analysis/stopping rules: After 15 evaluable subjects have been enrolled and treated (defined as having received scheduled treatment per protocol for at least 1 cycle and have completed restaging imaging) - an interim futility analysis will be conducted. If the objective response rate is less than 20% (3 of 15 subjects) or the median progression free survival is less than 6 months - enrollment will stop.

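### Do the comparative hypotheses in 3.1 and 3.2 require a fuller PFS analysis and power statement than section 7 gives?

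*Combined protocol and SAP*

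**What the plan says.** Section 3.1 sets PFS as the only primary endpoint, with the hypothesis of "improved progression free survival as compared with previously reported systemic therapies including pembrolizumab monotherapy, ipilimumab + nivolumab and tebentafusp". Section 3.2 repeats the pattern for two secondary endpoints: "improved objective response rate as compared with previously reported therapies including pembrolizumab monotherapy, ipilimumab + nivolumab and tebentafusp" and "improved overall survival as compared with previously reported therapies including pembrolizumab monotherapy, ipilimumab + nivolumab and tebentafusp".

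Section 7.1 then states: "As this is a single arm study, no formal statistical comparisons will be made". Section 7.2 again calls the study a signal-finding pilot and repeats the disclaimer. Its one power table, one-sided at 0.05 with 30 patients, concerns "the power for detecting a difference in the ORR compared with the historical average of 10% ORR with anti-PD-1 monotherapy". PFS enters section 7 twice: as a historical "median progression free survival of approximately 3.5 months" under PD-1 inhibitors, and in the interim rule, where enrollment stops "If the objective response rate is less than 20% (3 of 15 subjects) or the median progression free survival is less than 6 months". Section 7 gives no estimator, interval, censoring rule or expected precision for the final PFS analysis.

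**The concern.** Taken alone, 3.1 and 3.2 promise superiority over three regimens on three endpoints. Section 7 offers one power table, for a secondary endpoint, against one regimen, at the lower of the two benchmark rates that matter (10% for anti-PD-1 monotherapy, 18% for ipilimumab + nivolumab). The primary endpoint has no stated final analysis.

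Two of the hypotheses have no reference figure at all: section 4.1 gives no PFS for tebentafusp and no OS for pembrolizumab alone.

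The risk would be over-reading. A median PFS somewhat above 5.5 months could be presented as confirming 3.1 when 30 patients cannot support that, and the method of analysis could be chosen after the data are seen.

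**Working it through.** **Inputs.** N = 30, one-sided 0.05, historical ORR 10% and PFS 3.5 months (7.2). Enrollment 20 months, trial 48 months (1.0). From 4.1, pembrolizumab: "Two out of the 17 patients had an objective response (11.7%) and median PFS was 3.8 months". Also from 4.1: ipilimumab + nivolumab ORR 18%, PFS 5.5 months, OS 19.1 months; tebentafusp ORR 9%, OS almost 22 months. Assumed: exponential times, uniform accrual, all 30 enrolled, historical values fixed, interim rule ignored.

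**1. The plan's own table.** Power = Phi{[(p1 - p0) - 1.645 sqrt(p0 q0/n)] / sqrt(p1 q1/n)}. With p0 = 0.10, 1.645 x sqrt(0.09/30) = 0.0901.

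- p1 = 0.20: (0.10 - 0.0901)/0.0730 = 0.136, power 0.55
- p1 = 0.25: (0.15 - 0.0901)/0.0791 = 0.758, power 0.78
- p1 = 0.30: (0.20 - 0.0901)/0.0837 = 1.314, power 0.91

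These match the stated 0.55, 0.78 and 0.91. The table is correct for what it says it covers.

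**2. ORR against 18%.** By the same formula, 1.645 x sqrt(0.18 x 0.82/30) = 0.1154.

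- p1 = 0.25: (0.07 - 0.1154)/0.0791 = -0.574, power 0.28
- p1 = 0.30: (0.12 - 0.1154)/0.0837 = 0.055, power 0.52

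The exact binomial test needs 10 of 30 (P = 0.032 at 18%; 9 of 30 gives 0.076). Its power is 0.20 and 0.41.

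**3. Median PFS.** Expected events = 30 x {1 - [exp(-28L) - exp(-48L)]/(20L)}, L = ln 2/median. At a median of 6.0, L = 0.1155 and the result is 29.5; at 7.5 it is 29.0, and at 9.0 it is 28.2. Using 29, power = Phi[sqrt(29) ln(m1/m0) - 1.645], where sqrt(29) = 5.385.

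| True m1 | Reference m0 | ln(m1/m0) | Power |
|---|---|---|---|
| 6.0 | 3.5 | 0.539 | 0.90 |
| 6.0 | 3.8 | 0.457 | 0.79 |
| 6.0 | 5.5 | 0.087 | 0.12 |
| 7.5 | 5.5 | 0.310 | 0.51 |
| 9.0 | 5.5 | 0.492 | 0.84 |

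**4. OS.** The same formulas give 20.8 deaths at a true 22 months and 17.4 at 30 months. Power against 19.1 is 0.16 at 22 and 0.59 at 30; against 22 it is 0.36 at 30.

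**5. Precision that a report would show.** With 30 events and an observed median of 7 months, the approximate 95% CI is 7 x exp(+/-1.96/sqrt(30)) = 4.9 to 10.0 months, which includes 5.5. With 9 of 30 responders the exact 95% CI is 14.7% to 49.4%, which includes 18%.

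**6. Does a point estimate above 5.5 mean anything alone?** If the true median is 5.5 and event dates are exact, the sample median exceeds 5.5 about half the time: 0.43 if it is read at the 15th of 30 events, 0.57 at the 16th. That holds for any median and is no special fault of this design. The interval in step 5 guards against misreading.

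**7. Set against the text.** Section 7 claims only the power in step 1. It makes no power claim for PFS or OS, and none against ipilimumab + nivolumab or tebentafusp. Steps 2 to 4 therefore contradict no figure in the plan; they show what the disclaimer in 7.1 already implies.

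**The case for a change.** The best case for a change is that even an estimation study needs a method for its primary endpoint. Without one, the progression criterion, censoring and analysis set are open after the data are seen. The only set defined in section 7 is the interim evaluable set, which requires completed restaging imaging; used at the end, it could drop early deaths. The sample size is also described as resting on comparison with historical data, so the comparison is not wholly disclaimed.

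Part of this stands. The gap is genuine, and the document does not use one progression criterion throughout. But the pieces for a sensible analysis are there. Section 3.1 defines PFS from enrollment to progression or death. Section 6.1.4.4 names RECIST 1.1 for the date of progression, while 6.1.4.5 uses iRECIST for investigator assessment and treatment decisions. Section 6.1.4.3 shows where imaging follow-up ends, including at a new anticancer treatment. The evaluable definition is tied to the interim look. A Kaplan-Meier median with an interval in the enrolled patients is what most analysts would produce.

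A second argument concerns scan dating. In simulation with a true median of 3.5 months, the Kaplan-Meier lower 90% limit exceeds 3.5 in 57% of trials if every event is dated on the 9-week grid, 22% if half are dated exactly and 5% if all are. An interval-censored estimate would correct this, but it needs a distributional assumption. If the historical medians were themselves dated by scans, it could handicap the new regimen in the comparison. The documents do not give those schedules, so adding it is a debatable trade-off. A rule about whether such intervals exclude 3.5 to 3.8 months would also be a formal comparison, which section 7 rules out.

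**Conclusion.** The observation is correct but calls for no change. The hypotheses in 3.1 and 3.2 reach further than 30 patients can: power is 0.12 for a true PFS of 6.0 against 5.5 months, and exact power is 0.20 to 0.41 for ORR of 25% to 30% against 18%. The design does well against anti-PD-1 monotherapy PFS (0.90 against 3.5 and 0.79 against 3.8, at a true 6.0) and can detect a large gain over ipilimumab + nivolumab (0.84 at a true 9 months). Section 7 claims nothing beyond its ORR table and disclaims formal comparison, so the hypotheses read as scientific rationale. A descriptive median with its interval remains sound, and rewording 3.1 and 3.2 would add little to that disclaimer. Naming the estimator, censoring rules and precision, or labelling the ORR table as secondary, would be good housekeeping, but the conclusions do not depend on it.

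This rests on exponential times, uniform accrual, fixed historical values and full enrollment. The interim rule can stop the trial earlier: at a true ORR of 18%, the response criterion alone is failed with probability 0.48. It also assumes that the report follows section 7 and gives the historical figures as references only.
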